Central Council for Research in Homoeopathy New Delhi

STUDY PROTOCOL

HOMOEOPATHY AS ADJUVANT TO STANDARD TREATMENT PROTOCOL IN MANAGEMENT CORONA VIRUS INFECTION- A RANDOMISED, PLACEBO CONTROLLED, OPEN LEVEL STUDY

Version 2.0

Central Council for Research in Homoeopathy, New Delhi

Study Summary

| Title | Homoeopathy as adjuvant to standard treatment protocol in management coronavirus infection- a randomised, placebo controlled, open level study | | |
|--------------------------------------|---|--|--|
| Short Title/Public title | Homoeopathy as adjuvant in management coronavirus infection | | |
| Methodology | Randomised, Placebo Controlled, Open Level Study | | |
| Study Duration | 1 year | | |
| Study Center (s) | | | |
| Objectives | Primary Objectives: To assess and compare the effectiveness of homoeopathic treatment as an adjuvant to the standard treatment in coronavirus infection. Secondary objectives: To assess and compare time to fever clearance To assess and compare time to resolution of pneumonia To assess and compare severity of symptoms. To compare the period of hospital stay To assess and compare time to recovery | | |
| Number of Subjects | | | |
| Main Inclusion Criteria | Patients with corona virus infection reporting at Hospital, with all the following shall be included: | | |
| 151. | Laboratory confirmed cases of Corona virus infection. Age 18 years & above both sex | | |
| | 3. Willing to give signed written informed consent | | |
| Study Product | Indicated Homoeopathic medicines. Potency and dose will be given following hom. principles. | | |
| Protocol preparat - [name] | ion [name], Scientist-II, CCRH | | |

HOMOEOPATHY AS ADJUVANT TO STANDARD TREATMENT PROTOCOL IN MANAGEMENT CORONA VIRUS INFECTION- A RANDOMISED, PLACEBO CONTROLLED, OPEN LEVEL STUDY

Introduction

Background

The recent outbreak of the novel coronavirus (COVID-19) and its declaration as pandemic by the World Health Organisation has led to a major concern around the globe. On 31 December 2019, WHO was alerted about outbreak of several cases of pneumonia in Wuhan City, Hubei Province of China which raised concern because the affected patients were geographically linked with a local wet market as a potential source. One week later, on 7 January 2020, Chinese authorities confirmed that they had identified a novel coronavirus, named "COVID-19" from coronavirus family that also included Severe Acute Respiratory Syndrome coronavirus SARS-CoV) and Middle East Respiratory Syndrome coronavirus (MERS-CoV).1 Coronaviruses are zoonotic and detailed investigations found that SARS-CoV was transmitted from civet cats to humans and MERS-CoV from dromedary camels to humans.² The genetic sequence of the 2019 novel coronavirus (2019-nCoV) enabled the rapid development of point-of-care realtime RT-PCR diagnostic tests specific for 2019-nCoV which is based on full genome sequence data on the Global Initiative on Sharing All Influenza Data [GISAID] platform.3 Though scientist of China shared its genome sequence, the Australian scientists have for the first time recreated the virus.4

About the pandemic

So far, 1,83,047 globally confirmed cases are reported and 80,881 confirmed cases from China but 3,226 deaths making China "Very High" under WHO risk assessment.⁵ Till March 22, globally, approximately 303,000 confirmed cases, including more than 12,900 deaths in approximately 150 countries⁶. Person-to-person transmission of this novel coronavirus in hospital and family settings may be suggested, as reports of infected travellers in other geographical regions surface.⁷ As of 25th March in India, more than 600 cases reported from different states with 11 death⁸.

Pathogenesis

The pathological features of COVID-19 have been shown to greatly resemble those seen in SARS and MERS coronavirus infection.^{9, 10} Coronaviruses have a protein known as a replicase encoded in its genome which allows the RNA viral genome to be transcribed into new RNA copies using the host cell's machinery.¹¹ Coronaviruses have a non-structural protein – a protease – which can separate the proteins in the chain.^{12, 13} The excess production of type 2 cytokines and an age dependant defect in T-cell and B-cell function could lead to a deficit in control of viral replication and more prolonged proinflammatory responses, potentially leading to a poor outcome in patients of COVID-19.¹⁴

Clinical features

The 2019-nCoV infection has so far caused clusters of severe respiratory illness like severe acute respiratory syndrome coronavirus and was associated with ICU admission and high mortality in China. In a first-hand data reported from Hospital of China, it was found that, by Jan 2, 2020, 41 laboratory- confirmed 2019-CoV infection admitted hospital patients had a higher plasma level of IL2, IL7, IL10, GSCF, IP10, MCP1, MIP1A, and TNF α . Fever, cough, myalgia or fatigue is most common symptoms reported whereas less common symptoms include sputum production, headache, haemoptysis and diarrhoea. $^{15, 16}$

The Chinese CDC report¹⁷ divided the clinical manifestations of the disease by following three severities:

| S.No. | Disease | Symptoms | Occurred in % |
|-------|----------|---|---------------|
| | severity | | cases |
| 1. | Mild | Non-pneumonia and mild pneumonia | 81% |
| | Disease | | |
| 2. | Severe | Dyspnea, respiratory frequency ≥ 30/min, blood oxygen | 14% |
| | disease | saturation (SpO2) \leq 93%, PaO2/FiO2 ratio $<$ 300, and/or | |
| | | lung infiltrates > 50% within 24 to 48 hours | |
| 3. | Critical | Respiratory failure, septic shock, and/or multiple organ | 5% |
| | Disease | dysfunction (MOD) or failure (MOF) | |

Homoeopathic in epidemics

Currently there is no specific antiviral treatment or any vaccine against COVID-19 infection. In such a condition, WHO recommended that "it is ethical to offer unproven interventions with as yet unknown efficacy and adverse effects, as potential treatment or prevention" keeping in view no vaccine or anti-virals were available. 18 It is reported that India now has 126 confirmed cases of COVID-19 viral infection and India has reached the 2nd stage of pandemic which implies that the community transmission is expected within one month.19 Homoeopathy being the second most popular system of medicine has been successfully reported to have a positive role in preventing epidemic diseases. The preventive role of Homeopathy in epidemic diseases is well known and reportedly been used for prevention during the epidemics of Cholera, Spanish Influenza, Yellow fever, Scarlet fever, Diphtheria, Typhoid etc. There is anecdotal evidence that homeopathy was successful during the Spanish flu epidemic of 1918 to 1919, in which at least 20 million people died worldwide, more than 500,000 in the United States alone. According to the historian Julian Winston, the death rates for patients treated with homeopathy (genus epidemicus) were 1 to 2% compared with a 30 to 60% mortality for those treated by conventional physicians. 20, 21

In Indian scenario, CCRH had undertaken clinical trials in Dengue and Acute Encephalitis syndrome/JE with Homoeopathy as an add on to usual care in tertian care setups. In Dengue Hemorrhagic fever, add on Homoeopathy could bring early

improvement in platelet count and decrease in hospital stay by 2 days.²² Similarly, in Acute Encephalitis Syndrome/Japanese Encephalitis homeopathy as an adjuvant to the institutional management protocol could decrease death rate by 15% in comparison to those who received only Institutional Management protocol.²³ In both the studies, adverse effect was not observed. Keeping in view the clinical success in above mentioned severe viral diseases and in absence of any anti-virals and vaccine against CVID-19, Homoeopathy as an adjuvant may be tested in COVID-19 patients as an adjuvant to the usual care.

2. STUDY OBJECTIVES

Primary Objectives:

 To assess and compare the effectiveness of homoeopathic treatment as an adjuvant to the standard treatment in coronavirus infection.

Secondary objectives:

- i. To assess and compare time to fever clearance
- ii. To assess and compare time to resolution of pneumonia
- To assess and compare severity of symptoms.
- To compare the period of hospital stay
- v. To compare the use of conventional medication use.
- To assess and compare time to recovery

3. STUDY DESIGN

This shall be randomized, placebo controlled, open level study. Groups are as below:

- Group I: Standard conventional management + Homoeopathy
- Group II: Only Standard conventional management

3.1 Selection of patients

Inclusion criteria:

Patients with corona virus infection reporting at Hospital, with all the following shall be included:

- 1. Hospitalized patients with confirmed COVID-19
- 2. Age 18 years & above both sex
- 3. Willing to give signed written informed consent

Exclusion Criteria

- 1. Patients requiring ventilatory support
- 2. Immunocompromised patients

5

© Central Council for Research in Homoeopathy, New Delhi

- Severe heart, lung, kidney, brain, blood diseases or other important systemic diseases;
- **4**. Subjects were considered to be unable to complete the study, or not suitable for the study by researchers.
- 5. Women during pregnancy;

3.2 Primary endpoint

Clinical recovery of patient or death

4.3 Sample Size

Convenient sampling.

4.5 Study Duration

01 years

4.6 Study centers

5. STUDY DRUG/INTERVENTION

Patients will be prescribed individualized drug as per the presentation of each case. Details as below:

5.1 Intervention group:

5.1.1. Group I: Homoeopathic treatment Group-

Patients shall be prescribed homoeopathic medicines, selected based on totality of symptoms by the homoeopathic investigator as an add on to standard management of Covid-19.

5.1.2. Group II: Placebo Group-

Patients shall be prescribed placebo as an add on to standard treatment for management of Covid-19.

5.1.3 Randomization

The randomization will be done through computer generated randomization chart.

5.1.4 Blinding of Study Drug

The study will be open level study.

5.2. HOMOEOPATHIC INTERVENTION (Group I)

5.2.1. Procurement & dispensing of medicine

- Homoeopathic medicines in dilutions of centesimal potency (30C, 200C, and 1M) for the trial shall be procured from any of the approved Good Manufacturing Practices (GMP) firms.
- Globules/pills of size 30 shall be used for medicating dilutions and dispensing alcohol shall be used for preparing placebo resembling the medicine. These globules shall be procured from same firms. One dose will constitute 4 globules moistened with the medicine or placebo.
- Investigator/ pharmacist will dispense the homoeopathic medicine/placebo to the patients as per the randomization chart provided to him/her.

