5.2.2. Method of selection of individualized homoeopathy medicines

5.2.2.1. During acute crisis

After enrollment in the study, investigator will take the case on acute case recording format. Thereafter the investigator shall build totality of symptoms. Based on these symptoms, a group of medicines shall be evolved by the method reportorial/non-reportorial approach to the case. For this purpose, any repertory as per need of the case shall be used and all medicines mentioned against the selected rubric(s) in the repertory, irrespective of the grades thereof, will be considered. After repertorisation, however, only one medicine whose portrait confirms in the Materia Medica shall be selected as the first prescription with justification for the respective patient. The classical approach to prescribing need to be adopted and preferable prescription should be among drugs published in pharmacopoea.

[figure not shown]

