11. ETHICAL CONSIDERATIONS

This study is to be conducted according to standards of Good Clinical Practice. This trial will be conducted in accordance with the requirements of the Declaration of Helsinki 1964, the Revisions of Tokyo 1975, Venice 1983 Hong Kong 1989, Somerset West 1996, Edinburgh 2000, First clarification- Washington 2002, Second clarification- Tokyo 2004 & Seoul 2008.

This protocol and any amendments will be submitted to a properly constituted independent Ethics Committee (EC), in agreement with local legal prescriptions, for formal approval of the study conduct. As this will be placebo control randomized study consent of patient shall be taken after providing sufficient information for subjects to make an informed decision about their participation in this study.

This consent form will be submitted with the protocol for review and approval by the EC for the study. The formal consent of a subject, using the EC approved consent form, must be obtained before that subject undergoes any study procedure. The consent form must be signed by the subject or legally acceptable guardian/ head of family and the investigator-designated research professional obtaining the consent.

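### The investigator may hold the randomisation chart and no concealment step is described, so upcoming assignments can be foreseen and protection against selection bias is not assured

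*Protocol*

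**What the plan says.** - **Generation of the sequence (Protocol 5.1.3):** "The randomization will be done through computer generated randomization chart". The section says nothing more.
- **Handling of the list (Protocol 5.2.1):** "Investigator/ pharmacist will dispense the homoeopathic medicine/placebo to the patients as per the randomization chart provided to him/her". Either role may hold the chart. The clause does not say when the chart is handed over or how much of it the holder can see.
- **Blinding (Protocol 5.1.4):** "The study will be open level study".
- **Exclusion criterion 4 (Protocol 3.1):** "Subjects were considered to be unable to complete the study, or not suitable for the study by researchers". No objective standard is attached.
- **Who does what at entry:** Section 11 refers to the "investigator-designated research professional obtaining the consent" and requires consent before any study procedure. Section 5.2.2.1 states: "After enrollment in the study, investigator will take the case on acute case recording format". No section names the person who enrols.

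**The concern.** Randomisation prevents selection bias only if whoever decides on a patient's entry cannot foresee the assignment that patient would get. A random sequence is not enough if the list can be read in advance. Here a permitted holder of the list belongs to the team that judges suitability, and one exclusion rests on judgement alone. A patient with a poor outlook could be declared unsuitable, or entered later, because of the group that comes next.

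The groups would then differ in prognosis at entry. Every between-group comparison would be affected, including the primary endpoint in section 3.2 (clinical recovery or death). A larger sample does not shrink such a bias. The baseline comparisons in section 7 can neither detect nor remove selection on unmeasured prognosis. Analysis cannot restore concealment after patients have been entered, so this is a matter for the protocol rather than for a statistical analysis plan.

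**Working it through.** **Reading the sections together**

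1. *Can a person involved in entry hold the chart?* Yes. Section 5.2.1 names the investigator as an alternative to the pharmacist.
2. *Can that person or team influence entry?* The text permits it. Criterion 4 is applied by researchers, and consent is taken by someone whom the investigator designates. The text does not say that the chart holder and the person who decides on entry are the same.
3. *Is there a barrier between list and entry decision?* None is described in 5.1.3, 5.2.1 or elsewhere in the text: no central allocation, no sealed envelopes, no independent list holder, no rule that eligibility and consent are recorded before the assignment is seen. The consent rule in section 11 gives some ordering, but it does not stop anyone from looking ahead on a list. The flow chart (Figure 1) was not available for this check.
4. *Does open-label treatment excuse this?* No. Assignments can be concealed until entry in a trial without blinding.

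**Illustration of size**

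The protocol has no figure to reproduce. Section 4.3 gives only "Convenient sampling" in place of a sample size, and no recovery rate is stated.

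Inputs:
- Severity mix from the table under Clinical features in the Introduction: 81% mild, and 14% + 5% = 19% severe or critical.
- Assumed recovery: 85% in mild disease, 50% in severe or critical disease, the same in both groups (no treatment effect).
- Assumed fraction *f* of severe or critical patients due for Group I who are passed over: one quarter or one half. Nobody due for Group II is passed over.

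Formulas:
- Severe share in Group I = 0.19(1 − f) / [0.81 + 0.19(1 − f)]
- Recovery = (1 − share) × 0.85 + share × 0.50

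| | Severe share | Recovery |
|---|---|---|
| Group II | 19% | 0.81 × 0.85 + 0.19 × 0.50 = 78.4% |
| Group I, f = 1/4 | 0.1425 / 0.9525 = 15.0% | 0.850 × 0.85 + 0.150 × 0.50 = 79.8% |
| Group I, f = 1/2 | 0.095 / 0.905 = 10.5% | 0.895 × 0.85 + 0.105 × 0.50 = 81.3% |

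Before rounding, the false gain is 1.4 points for f = 1/4 and 3.0 points for f = 1/2. It is zero if nobody is passed over.

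The gain equals the difference in severe share times the gap in recovery. For f = 1/2 this is (0.190 − 0.105) × (0.85 − 0.50) = 0.085 × 0.35 = 3.0 points. Halving the assumed gap to 0.175 halves the gain to 1.5 points. Passing over patients due for Group II instead reverses the sign. Sample size does not enter the formula.

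**The case against.** The strongest reply is that section 5.2.1 is a dispensing clause. Dispensing follows enrolment, so the clause does not prove that anyone sees an assignment early. It names a pharmacist as an alternative, and a pharmacist with no part in enrolment could keep the allocation concealed under the present wording. The protocol also does not say that the investigator enrols patients or applies criterion 4. All of this stands.

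A reader might infer that the investigator is given the complete chart, that the next allocation is therefore known before enrolment, and that the randomisation offers no protection. The documents do not support that. They do not say how much of the chart is visible or when, and they leave the roles open. What they support is that foreknowledge is permitted and nothing described prevents it.

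It is also fair to object that the illustration rests on assumed rates. The 81/19 split comes from a report of cases in China, whereas this trial enrols hospitalised patients, which may raise the severe share. Excluding patients who need ventilatory support lowers it. The net error in the 19% is unknown. This limits the numbers; the defect does not depend on them.

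**Conclusion.** The point holds in this form: the protocol allows the investigator or a pharmacist to hold the randomisation chart in an open-label trial with a discretionary exclusion, and its text describes no allocation concealment. Upcoming assignments can be foreseen before eligibility and consent are settled, so protection against selection bias is not assured. It does not follow that the bias will occur.

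No size can be fixed from the protocol. The 1.4 to 3.0 points are illustrative. They depend on the assumed recovery rates, the assumed pass-over fractions and direction, and a severity mix taken from another population. The matter should still be settled before enrolment, because any selection at entry cannot be undone in the analysis.

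**What to change.** Amend sections 5.1.3 and 5.2.1 as follows:

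- The chart is generated and held by someone who neither enrols nor assesses patients: the sponsor's office, or a pharmacist with no part in enrolment.
- Assignments are released one at a time, by sequentially numbered opaque sealed envelopes or by telephone, and only after consent and eligibility have been recorded.
- Any exclusion under criterion 4 is logged with its reason before an assignment is released.
- The investigator may dispense after release but does not hold the chart.

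Packs numbered in advance would not suit this design, because sections 5.2.2.1 and 5.4 have the medicine chosen individually after enrolment and allow it to change later.

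The cost is the envelopes or calls, a short delay at enrolment, and a named list holder. Section 4.6 lists no centres, so it should not be assumed that every site has an independent pharmacist. Where there is none, the sponsor's office can hold the list. Blinding is not needed.

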5.2.2. Method of selection of individualized homoeopathy medicines

5.2.2.1. During acute crisis

After enrollment in the study, investigator will take the case on acute case recording format. Thereafter the investigator shall build totality of symptoms. Based on these symptoms, a group of medicines shall be evolved by the method reportorial/non-reportorial approach to the case. For this purpose, any repertory as per need of the case shall be used and all medicines mentioned against the selected rubric(s) in the repertory, irrespective of the grades thereof, will be considered. After repertorisation, however, only one medicine whose portrait confirms in the Materia Medica shall be selected as the first prescription with justification for the respective patient. The classical approach to prescribing need to be adopted and preferable prescription should be among drugs published in pharmacopoea.

[figure not shown]
5.2.2.2 Prescription details

| I. | Prescription | Prescription will be the indicated medicine in centesimal potency (30C/200C/1M). |
|------|--------------|---|
| II. | Dosage | Four pills of size 30 globules in the required potency. |
| III. | Repetition | Indicated medicine will be repeated as per the need of each case. Repetition can be done 2 to 6 hourly or even oftener, depending upon the intensity of symptoms. |

7. STATISTICAL PLAN & SUBJECT COMPLIANCE MONITORING

The overall significance level of the primary outcome will be explorative. All the data shall be assessed for normal distribution. Comparison of the baseline characteristics will use standard parametric/nonparametric statistical techniques, such as Fisher's exact test for categorical data, and the Kruskal-Wallis test for ordinal data and parametric tests for continuous data.

7.1 Steps to Maximize Adherence and Retention

- All the participants shall be motivated to adhere to study treatment and for measurement of various investigations from time to time by the investigator.
- Patients will be asked to contact the investigator for any problems faced by them during the study period.

7.2 Prior and Concomitant Therapy

As study intervention is adjuvant to conventional medicine, patients will continue taking conventional treatment as per standard treatment protocol. Other than intervention patients shall not take any other intervention or herbal treatment for disease.

8. SAFETY AND ADVERSE EVENTS

a. Recording of Adverse Events

At each contact with the subject, the investigator must seek information on adverse events by specific questioning and, as appropriate, by examination. Information on all adverse events should be recorded immediately in the source document, and in the appropriate adverse event module of the case report form (CRF). All clearly related signs, symptoms, and abnormal diagnostic procedures results should be recorded in the source document, though should be grouped under one diagnosis.

All adverse events occurring during the study period must be recorded. The clinical course of each event should be followed until resolution, stabilization, or until it has been determined that the study treatment or participation is not the cause. Serious adverse events that are still ongoing at the end of the study period must be followed up to determine the final outcome. Any serious adverse event that occurs after the study period and is considered to be possibly related to the study treatment or study participation should be recorded and reported immediately.

b. Stopping Rules

Should the trial be terminated prematurely, as far as possible each individual patient should undergo a complete final examination or at least a final telephone interview, regarding the state of the patient's health, and if necessary, from the point of view of drug safety and validity of the trial results.

c. Medical Monitoring

It is the responsibility of the study team to oversee the safety of the study at his/her site. This safety monitoring will include careful assessment and appropriate reporting of adverse events, as well as the construction and implementation of a site data and safety-monitoring plan. Medical monitoring will include a regular assessment of the number and type of serious adverse events.

